6.1.2. Measurement and calculation of outcomes

For the diagnostic study we calculated cardiac index, which was derived from cardiac output. Cardiac output has been measured with the cardiac probe M3S of M4S with default cardiac imaging setting of the General Electric Vivid-S6 mobile ultrasound machine. Two views were obtained: the parasternal long axis (PLAX) and the apical five chamber view (AP5CH). The PLAX was used as the primary view to measure the left ventricular outflow tract (LVOT) diameter. The AP5CH view was used to measure the velocity time integral (VTI) using the pulse wave Doppler signal in the LVOT. Cardiac output was calculated on the ultrasound machine according to the formula:

$$\text{Cardiac output } \left(\frac{L}{\text{min}}\right) = \text{heart rate} \cdot \text{VTI} \cdot \pi \cdot \left(\frac{1}{2} \cdot \text{LVOT}\right)^2$$

At a later time, the images and measurements were validated by technicians from an independent core laboratory, whom were blinded for all other measurements and outcomes.

We used cardiac index instead of cardiac output for interindividual comparisons. Cardiac index is the cardiac output adjusted for body surface area:

$$\text{Cardiac index } \left(\frac{L}{\text{min}}\right) = \frac{\text{Cardiac output}}{\text{Body surface area}}$$

Where body surface area was calculated with the DuBois formula (14):

$$\text{Body surface area} = 0.007184 \cdot \text{Weight}^{0.425} \cdot \text{Height}^{0.725}$$

Cut-offs for a low cardiac index for critically ill patients are inconsistent (15). Haemodynamic criteria to diagnose cardiogenic shock vary from a cardiac index of 1.8 to 2.5 L/min/m² (16-19). A cardiac index below 2.2 L/min/m² is often used to diagnose a low cardiac output syndrome after cardiac surgery (20), whereas a large clinical trial used a cut off below 2.5 L/min/m² in patients with acute lung injury (19). These criteria, however, apply to patients with heart failure or after cardiac surgery. There currently is no consensus on how much cardiac index is low, normal or high for the critically ill patient. In the secondary outcome of our diagnostic study, we will both use a cut-off of 2.2 and 2.5 L/min/m² for a low, and a cut-off of 4.0 and 4.5 L/min/m² for a high cardiac index.

For the prognostic study we obtained follow-up on all-cause mortality from the municipal personal records database. Analysis of mortality will be performed using time-to-event data (patients were censored at 90-days of follow-up).

6.2. Analysis methods

6.2.1. Correlations

We will use the Pearson *r* correlation and Spearman correlation coefficient rho (*r*) to evaluate the degree of relationship between variables. For normally distributed variables, we will use the Pearson *r* correlation with 98.5% confidence interval upon checking for linearity and homoscedasticity, while in case of skewed, ordinal data, the degree of association between variables will be quantified using Spearman correlation coefficient rho (*r*). We will use Cohen's *d* to evaluate the correlation coefficient and assess the strength (or effect size) of the relationships, where a correlation coefficient between

0.10 and 0.29 will represent a small association, between 0.30 and 0.49 a medium association, and a coefficient of 0.50 and above a large association.

6.2.2. *Continuous and dichotomous outcomes (diagnostic study)*

We will conduct a least-squares linear regression analysis for continuous dependent variables and a logistic regression for dichotomous dependent variables. A univariable regression analysis will be conducted on 17 clinical examination findings with cardiac index as the dependent variable. A univariable regression analysis will be conducted on all variables and a $p < 0.25$ will be used for inclusion in the multivariable model. As there are no previous studies that include (a combination of) all available clinical examination variables into one model estimating cardiac index, we will not include any variable on a theory driven basis. We will construct the multivariable model using forward stepwise regression by adding blocks of variables. In case of a multivariable linear regression model, we will construct a kernel density plot to assess normality of the residuals and check the homogeneity of variance by plotting the residuals versus the fitted values. We will use the variance inflation factor (VIF) to check for multicollinearity; as a rule of thumb, we will assume multicollinearity when a variable has a VIF-value greater than 10. If the assumptions are not met, we will use an ordinal regression analysis.

6.2.3. *Time-to-event data (prognostic study)*

Analysis of mortality will be performed using time-to-event data (patients were censored at 90-days of follow-up). Categorical variables will be analysed using the log-rank test and continuous variables will be assessed using a univariable Cox proportional hazard regression analysis. Analysis of mortality proportion will be presented by Kaplan-Meier survival curves when independent variables are dichotomous or categorical. A univariable Cox regression analysis will be conducted on 22 clinical examination, haemodynamic and biochemical variables with 90-day mortality as the dependent variable. Covariates with a $p < 0.25$ in the univariable analysis will be included in the multivariable model. We will include the SAPS-II score in our multivariable Cox regression model of 90-day mortality. The SAPS-II is a predictive score for in-hospital mortality and includes seventeen covariates among which age, haemodynamic and biochemical variables, and presence of metastatic or haematological cancer (21). The proportionality assumption will be tested by using the Schoenfeld and scaled Schoenfeld residuals. We will test the proportionality of the model as a whole and the proportionality for each predictor and reject proportionality in case of significant test findings ($p < 0.05$). We will plot graphs of the scaled Schoenfeld assumption, where horizontal lines in the graph indicate that the proportionality assumption is not violated. We will also construct log-log plots, where two parallel lines indicate that proportionality was not violated. The goodness of fit of the final model will be evaluated

by using the Cox-Snell residuals. In our Cox regression models, at least 15 events are necessary for each variable included in the final model (22,23).

6.2.4. *Validation (both)*

Because of the fixed sample size of our study, we will use bootstrapping validation to assess the accuracy of our model. We will randomly select 1075 individuals from the dataset with replacement, build our model on the bootstrapped sample and validate it on the original data. We will repeat this process 100 times and include a variable into our final model if it was significant in at least 80 models. We will still emphasise the hypothesis-generating aspect of our findings. We aim to validate our findings in an independent cohort in the future.

6.3. **Sensitivity and subgroup analyses**

In the diagnostic study, we will conduct a sensitivity analyses on the subgroup of patients in which the quality of the cardiac output measurements by CCUS by the core laboratory is considered 'good'.

In the prognostic study, we will conduct a sensitivity analyses on different follow-up times of mortality: we will also use mortality at 7 and 30 days.

If the sample size permits, we will conduct subgroup analysis in different subpopulations. We will create the following subgroups in the basic study and test both our prognostic and diagnostic hypotheses on:

- Subgroup 1: subdivide the population into three groups: no shock, shock associated with a low cardiac output, shock associated with a high cardiac output.
- Subgroup 2: subdivide the population by underlying pathologies that could influence the haemodynamic measurements in a patient: Patients admitted due to cardiac arrest, heart failure, after liver transplantation or liver failure, central nervous system pathologies, and septic shock. We will identify clinical subgroups by using variables such as APACHE-IV admission diagnoses, confirmed infection, cardiac arrest from the Dutch National Intensive Care Evaluation (NICE) registry. The NICE registry contains good quality and complete data due to several assurance quality procedures (24). Patients with septic shock are identified using the quick Sequential Organ Failure Assessment (qSOFA) score combined with a confirmed infection according to the latest definition (25).

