6.5. Additional analyses: diagnostic test accuracy

6.5.1. Relationship between clinical examination signs and cardiac index

There is currently no consensus on how much cardiac index is sufficient for the critically ill patient. Different studies used differing cut-offs for a low cardiac index (15). Therefore, we will use 2 cut-offs for both a low and high cardiac index:

1. Cut-offs for a low cardiac index: 2.2 and 2.5 L/min/m²
2. Cut-offs for a high cardiac index: 4.0 and 4.5 L/min/m²

We will conduct a logistic regression with the dichotomised cardiac index and an ordinal logistic regression with a categorical cardiac index as the dependent variable. A univariable analysis will be conducted on all dependent (clinical examination) variables and a $p < 0.25$ will be used for inclusion in a multivariable model. Calibration of our multivariable model will be checked with a Hosmer-Lemeshow test and by plotting observed proportions of cardiac index against the predicted risks of 10 equally sized groups. We will identify the cardiac index cut-off(s) where clinical examination has the best discriminative value based on the area under the receiver operating characteristic (ROC)-curves.

Based on the multivariable logistic regression findings, we will construct a risk score for cardiac index based on the coefficients in the model. Scores will be calculated by dividing all coefficients by the lowest coefficient or by transforming all coefficients so that the score is easy to count.

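### Section 6.2.2 gives one fallback, ordinal regression, for all failed linear-model checks: it cannot remedy a VIF above 10, and its outcome coding is not defined

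*SAP*

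**What the plan says.** SAP section 6.2.2 describes the primary diagnostic analysis, a least-squares regression of cardiac index on clinical examination findings. Seventeen findings are screened one at a time at p < 0.25. No variable is included on theoretical grounds, and the multivariable model is built forward in blocks.

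Three checks follow:

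- Normality: "we will construct a kernel density plot to assess normality of the residuals".
- Variance: "check the homogeneity of variance by plotting the residuals versus the fitted values".
- Collinearity: "as a rule of thumb, we will assume multicollinearity when a variable has a VIF-value greater than 10".

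The next sentence is the only remedy: "If the assumptions are not met, we will use an ordinal regression analysis". It does not say which check triggers it, how cardiac index is to be coded, or what happens to a collinear variable.

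The only ordinal model of cardiac index that the SAP describes is in section 6.5.1: "an ordinal logistic regression with a categorical cardiac index as the dependent variable". Its cut-offs are listed there as "Cut-offs for a low cardiac index: 2.2 and 2.5 L/min/m²" and "Cut-offs for a high cardiac index: 4.0 and 4.5 L/min/m²". Section 6.1.2 assigns them to the secondary outcome of the diagnostic study.

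**The concern.** A single remedy has been attached to problems of different kinds. Non-normal or unevenly spread residuals concern the outcome given the predictors, so changing the outcome model is at least a relevant response. Collinearity concerns the predictors alone. Refitting the same predictors with an ordinal outcome leaves the unstable coefficients as they were and also gives up the linear model.

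The trigger could well occur. Section 5.6 acknowledges that most of the measured variables are correlated. Table 2 lists capillary refill at three sites, central temperature, peripheral temperature at two sites, and the central-to-peripheral temperature difference. That difference is an exact linear function of central temperature and the peripheral temperature it is taken from. Entering all three makes VIF unbounded and leaves no unique least-squares solution. The p < 0.25 screen is univariable and so cannot prevent this.

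The second issue is the unnamed coding. An analyst who reaches the fallback must choose it after seeing residual plots, and the choice makes a material difference to precision.

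**Working it through.** **Inputs.** From SAP section 3.2.1: N = 1075, SD of cardiac index 0.99, SD of urine output 0.98, pilot slope 0.040, true slope 0.10, alpha 0.015 (two-sided, critical value 2.43), stated power 0.81. From section 6.5.1: cut-offs 2.2, 2.5, 4.0 and 4.5. Assumed, because the SAP does not give it: mean cardiac index 2.6 to 3.5, with a normal distribution.

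**Step 1: the SAP's own power.**
- Residual SD = √(0.99² − (0.040 × 0.98)²) = 0.989.
- Noncentrality = 0.10 × 0.98 × √1075 / 0.989 = 3.25.
- Power ≈ Φ(3.25 − 2.43) = 0.79, against the stated 0.81. This agrees within two points and serves as the baseline.

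**Step 2: does ordinal regression relieve collinearity?** For two predictors with correlation 0.96, VIF = 1/(1 − 0.96²) = 12.8, whatever the outcome model. In 60 simulated data sets (N = 1075, mean 3.0, cut-offs 2.5 and 4.5), the variance of the first coefficient, relative to a model with that predictor alone, rose as follows:

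| Model | Variance inflation |
|---|---|
| Least squares | 12.7-fold |
| Ordinal logit | 12.6-fold |

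The switch gives no relief.

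**Step 3: what the unnamed coding costs.** The share of information kept when a normal outcome is grouped is the sum over categories of (φ(lower) − φ(upper))² / p, where p is the category probability and the limits are standardised.

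Example with mean 3.0 and cut-offs 2.5 and 4.5:
- Standardised limits are −0.505 and 1.515, with densities 0.351 and 0.127.
- Category probabilities are 0.307, 0.628 and 0.065.
- Share kept = 0.351²/0.307 + (0.351 − 0.127)²/0.628 + 0.127²/0.065 ≈ 0.40 + 0.08 + 0.25 = 0.73.
- Power ≈ Φ(3.25 × √0.73 − 2.43) ≈ 0.63.

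Over all four low/high cut-off pairs and assumed means 2.6 to 3.5, with probit and proportional-odds versions taken together:

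| Coding of cardiac index | Information lost | Power, urine output |
|---|---|---|
| Linear model | none | 0.79 |
| Ordinal, ungrouped (share kept 3/π = 0.955) | about 4.5% | 0.77 |
| Ordinal, all four cut-offs (five categories) | 15-20% | 0.68-0.71 |
| Ordinal, three categories | 20-33% | 0.59-0.68 |

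For capillary refill time (SD 2.4), the same true slope gives noncentrality 0.10 × 2.4 × √(1075 × 0.67) / 0.99 = 6.5 even at the largest of these losses, so power stays at 1.00. The loss affects weaker predictors.

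**The case against.** **VIF may not be meant as a trigger.** Absence of collinearity is not strictly a linear-model assumption, and the SAP calls the threshold of 10 a rule of thumb. The fallback could refer only to normality and variance. This stands as a possible reading. It does not rescue the text, because the SAP then checks VIF and states no action.

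**Joint entry is not certain.** The 17 findings are not itemised and no correlations are reported, so a VIF above 10 is a risk that the plan leaves open, not an established event.

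**A fixed information loss cannot be claimed.** A reader might infer that the fallback discards about a quarter of the information on the SAP's own categories. The SAP does not support that: it never links the section 6.5.1 cut-offs to this fallback and does not give the mean of cardiac index. The calculation also assumes normality, which may be the condition that failed. Only a conditional range is defensible.

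**A different question?** A reader might also infer that an ordinal model abandons the primary question. Sections 2.2.2 and 6.1.1 define that question only as an association, with no effect scale in L/min/m² per unit. An ordinal model still tests association, although it reports odds ratios.

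**Ordinal regression for poor residuals is defensible.** Preferring robust standard errors there is partly a matter of taste, and the point does not rest on it. The study also describes its results as hypothesis-generating, which lowers the stakes.

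**Conclusion.** The point holds in a limited form. Section 6.2.2 has no workable rule for collinearity: on the natural reading it prescribes a remedy that cannot work, and on the narrower reading it prescribes nothing. This conclusion needs no assumption about the data, since VIF is a property of the predictors.

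The fallback is also incompletely specified. The unstated coding leaves room for anything from a negligible loss to about a third of the information, given a normal outcome with SD 0.99 and an assumed mean of 2.6 to 3.5. The power figures apply to the SAP's univariable urine output example, not to the multivariable model itself. The documents do not show that the primary analysis will be weakened, only that the plan does not prevent it.

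**What to change.** Replace the single fallback sentence in section 6.2.2 with separate rules.

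1. **VIF above 10:** drop or combine the collinear predictors and keep the linear model. State in advance which go together; for example, central temperature, peripheral temperature and their difference are not entered jointly. State likewise how the three capillary refill sites are handled if they prove collinear.
2. **Poor residual plots:** keep least squares with heteroscedasticity-consistent standard errors. If the ordinal model is retained instead, fit it to ungrouped cardiac index and check proportional odds.
3. **Grouped cardiac index:** confine it to the secondary accuracy analysis in section 6.5.

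The cost is SAP wording only; no data collection or sample size changes.

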3.2.1. Diagnostic study

We are planning our main analysis with 1075 patients in which we will regress their values of cardiac index against clinical examination findings. For this power calculation, we used the clinical examination variables urine output and capillary refill time as an example (7). In our design paper, the SD of cardiac index was 0.99 and the SD of urine output was 0.98, with a slope estimate of 0.040 obtained when cardiac index was regressed against urine output. The SD of capillary refill time was 2.4, with a slope estimate of -0.045 obtained when cardiac index was regressed against capillary refill time. If the true slope of the line obtained by regressing cardiac index against urine output or capillary refill time is 0.10, we will be able to reject the null hypothesis that this slope equals zero with probability (power) 0.81 for urine output, and 1.00 for capillary refill time. The type I error probability associated with this test of this null hypothesis is 0.015 (see paragraph 6.6 below).

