4.3. Adherence and protocol deviations

4.3.1. *Definitions of protocol deviations*

Protocol deviations are defined when the activities on a study diverge from the local institutional review board-approved protocol, however without significant consequences (13).

4.3.2. *Protocol deviations to be summarised*

We opted for the following subgroup analyses in our study protocol: different types of shock (distributive, obstructive, hypovolemic, cardiogenic), CVVH, heart failure by any cause, myocardial infarction, atrial fibrillation or surgery versus no-surgery patient groups.

We decided to replace these proposed subgroup analyses by the subgroups described in section 6.3. We believe that these subgroups agree better with the perspective from which a physician approaches a critically ill patient.

5. Study population

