6.1. Outcome definitions

6.1.1. Primary and secondary outcomes

The research questions and the design of the study have been published (7). We elaborate on the outcomes of the basic study below and described the primary outcomes of each sub-study in appendix 1.

The outcomes of research question 1, i.e. the diagnostic study, are:

- Primary: the association of a single or combination of clinical examination findings with cardiac index measured by CCUS
- Secondary: the diagnostic test accuracy of a single or a combination of clinical examination findings to diagnose a low, normal and high cardiac index
- Secondary: the association and diagnostic test accuracy of a single or combination of clinical examination findings with cardiac index in clinically different patient subgroups

The outcomes of research question 2, i.e. the prognostic study, are:

- Primary: the association of all measured clinical examination, biochemical and haemodynamic variables with 90-day mortality
- Secondary: the association of clinical examination, biochemical and haemodynamic variables with 7-day and 30-day mortality
- Secondary: the association of clinical examination, biochemical and haemodynamic variables that are not visible to caregivers with 90-day mortality
- Secondary: the association of clinical examination, biochemical and haemodynamic variables with 90-day mortality in clinically different patient subgroups

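### Subgroup 1 is split by low and high cardiac output without a stated rule, and the cardiac index hypotheses are then tested inside it; if the split uses measured output or index, those subgroup results are attenuated by construction (minor)

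*SAP*

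**What the plan says.** Section 6.3 introduces the subgroups with "We will create the following subgroups in the basic study and test both our prognostic and diagnostic hypotheses on". The first is "Subgroup 1: subdivide the population into three groups: no shock, shock associated with a low cardiac output, shock associated with a high cardiac output". Nothing further is said about how a patient enters a class. The second subgroup, by contrast, has named sources: "We will identify clinical subgroups by using variables such as APACHE-IV admission diagnoses, confirmed infection, cardiac arrest", among others, from the national intensive care registry.

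Section 6.1.1 makes the subgroup work a named secondary outcome of the diagnostic study: "the association and diagnostic test accuracy of a single or combination of clinical examination findings with cardiac index in clinically different patient subgroups". Section 6.1.2 explains the dependent variable: "Cardiac index is the cardiac output adjusted for body surface area". Sections 6.1.2 and 6.5.1 give cut-offs of 2.2 and 2.5 (low) and 4.0 and 4.5 L/min/m² (high). These are for index, serve the secondary accuracy outcome, and are not linked to Subgroup 1.

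Section 4.3.2 records that the study protocol had proposed "different types of shock (distributive, obstructive, hypovolemic, cardiogenic" among its subgroups, and then: "We decided to replace these proposed subgroup analyses by the subgroups described in section 6.3". Table 2 lists a shock type for the basic study but does not tie it to Subgroup 1. Section 6.3 makes the subgroup analyses conditional on sample size, and section 7 calls them exploratory.

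**The concern.** Cardiac index is cardiac output divided by body surface area, so a class defined by measured output or index is defined by the outcome of the regression run inside it. Truncating the outcome compresses its variance and pulls slopes, correlations and areas under the ROC curve toward the null. A sign with a real association of the planned size could then look uninformative in both shock classes merely because of how they were formed. At least three rules fit the text (index, output, clinical label). They give quite different results, and the SAP leaves the choice open until after the data are seen.

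**Working it through.** **Inputs from SAP 3.2.1.** N = 1075; SD of cardiac index 0.99; SD of urine output 0.98; SD of capillary refill 2.4; alpha 0.015. The planning case is "If the true slope of the line obtained by regressing cardiac index against urine output or capillary refill time is 0.10". Only the size of the slope matters below.

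**Assumed, because the SAP does not give them.** Normal distributions; the same slope in shock; mean index 2.4 to 3.3; one-third of the cohort in shock (the background figure in section 2.1), so about 358 patients; body surface area 1.95 (SD 0.22).

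**1. The plan's own power.** Urine output: 0.10 × 0.98 × √1075 / 0.99 = 3.246. Subtracting 2.432 (two-sided 0.015) leaves 0.813, so power is 0.79 against the stated 0.81. Capillary refill gives 1.00, as stated. The inputs are sound.

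**2. Index cut, one case worked.** Capillary refill has r = 0.10 × 2.4 / 0.99 = 0.242 and r² = 0.0588. Take mean index 2.8 and the class below 2.5.
- a = (2.5 − 2.8) / 0.99 = −0.303; λ = φ(a)/Φ(a) = 1.000.
- Remaining share of outcome variance: k = 1 − aλ − λ² = 0.303.
- Slope = 0.10 × k / (1 − r²(1 − k)) = 0.0303 / 0.959 = 0.032.
- Within-class r = √(r²k / (1 − r²(1 − k))) = 0.136.
- Class size 358 × 0.381 = 136. Power (noncentral t, noncentrality r√n / √(1 − r²)) is 0.20, against 0.68 at the same n with r = 0.242.

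**3. Index cut, range over means 2.4–3.3.**

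| Class | Capillary refill slope | Urine output slope |
|---|---|---|
| Low (<2.2 or <2.5) | 0.020–0.040 | 0.019–0.039 |
| High (>4.0 or >4.5) | 0.011–0.025 | 0.011–0.024 |

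For the class below 2.5 and means 2.6 to 3.0 (n about 110 to 165), capillary refill power is 0.14–0.28, against 0.56–0.77 at the same n without truncation.

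**4. Accuracy under an index cut.** Inside <2.5 only the 2.2 cut-off still separates patients; inside >4.0 only 4.5 does; inside <2.2 or >4.5 none does. By simulation for r = 0.242, the area at 2.2 is 0.61–0.63 in all patients and 0.55–0.56 inside <2.5. At 4.5 it is 0.63–0.67 in all and about 0.55 inside >4.0. On the section 6.5.2 scale that moves from poor to fail. At r = 0.10, or at the pilot slopes (|r| 0.04 and 0.11), it is below 0.60 throughout and no grade changes.

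**5. Output cut.** With thresholds at the index cut-offs × 1.95, simulated capillary refill slopes are 0.027–0.046 (low) and 0.026–0.037 (high). Output also contains body size. With no true association with index, a sign correlated 0.25 with body surface area (assumed) shows a within-class r with index of about −0.07 to −0.13 (mean index 2.6 to 3.0).

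**6. Clinical label** (lower half of shock patients, simulated).

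| How the label is formed | Capillary refill slope |
|---|---|
| Correlates 0.3–0.5 with index, tested sign not used | 0.084–0.095 |
| Correlates 0.9 with index, tested sign not used | 0.05 |
| Index 0.3 and tested sign 0.3 | 0.071 |
| Index 0.5 and tested sign 0.3 | 0.046 |
| Index 0.5 and tested sign 0.5 | 0.012 |

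For urine output the last three rows become 0.034, −0.017 and −0.10.

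**The case against.** The strongest reply is that the SAP never says the classes are cut on measured output. The replaced subgroups were clinical shock types, section 4.3.2 appeals to the physician's perspective, section 6.1.1 speaks of clinically different patients, and a shock type was recorded. On that reading the classes merely regroup shock types. This stands in part: a reader might infer that the SAP commits to selecting on its outcome, and the documents do not go that far. But the classes are named by cardiac output, and no sentence points to a label.

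Nor is the label a safe answer. Section 2.1 describes shock as diagnosed from clinical, haemodynamic and biochemical variables, so a label may be built from the signs under test. The SAP does not say whether it was assigned without the ultrasound result. Its place under the three-day column of Table 2 does not settle timing, because admission date and arterial blood gases sit there too.

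Class size is a fair objection as well. With 358 patients in shock, index above 4.0 leaves only 19 to 86 patients, and untruncated power for capillary refill is then just 0.08–0.44. In the high class, and for a weak sign such as urine output in any class, size already limits power. The condition on sample size in section 6.3 partly covers this. The additional power loss from truncation is seen mainly for capillary refill in the low class.

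**Conclusion.** The point holds as a minor one. Section 6.3 does not define its Subgroup 1 classes, yet tests the index hypotheses inside them. If they are cut on measured output or index, a true slope of 0.10 shrinks to about 0.01–0.04 (index) or 0.03–0.05 (output), and low-class power for capillary refill falls well beyond the loss from smaller n. The figures rest on normality and on the assumed mean index, body surface area and shock share; the SAP gives no index distribution or class sizes for patients in shock.

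Two stronger readings are not supported. The full-cohort primary diagnostic analysis is untouched, and the affected analyses are conditional, secondary and declared exploratory. Nor is a clinical label shown to remove the problem.

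The harm should not be understated either. An output cut can create associations for signs related to body size. In the prognostic study, cardiac output is itself among the measured haemodynamic variables, so its range is restricted within such classes.

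**What to change.** Amend section 6.3 as follows.
- The diagnostic (cardiac index) hypotheses are not tested within classes cut on ultrasound cardiac output or index.
- State which recorded variable defines absence of shock and each shock class, and where shock with mid-range output goes.
- If the recorded shock type is used, report that it may share information with the tested signs and with the ultrasound measurement.
- If an output-based split is kept for the prognostic hypotheses, state its measurement and cut-offs, and do not interpret cardiac output or index as a predictor within those classes.

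The cost is SAP wording only. The diagnostic study gives up results by measured low or high output.
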